Protocol Cover Page

Protocol Title: Development and Validation of a Cloak Shaped Device for Sham Pediatric Tuina

NCT Number: NCT03474172

Protocol Date: April 20, 2018

Version: Version 3 (final)

Principle [name] M.D.

Investigator

Leading [name] 2nd Affiliated Hospital of Guangzhou University of Chinese Medicine

Authors [name] 2nd Affiliated Hospital of Guangzhou University of Chinese Medicine

Other [name] Guangzhou University of Chinese Medicine

Authors [name] 2nd Affiliated Hospital of Guangzhou University of Chinese Medicine

[name] 2nd Affiliated Hospital of Guangzhou University of Chinese Medicine

[name] Dongguan Kanghua Hospital

[name] Guangzhou University of Chinese Medicine

[name] Dongguan Kanghua Hospital

[name] Guangzhou University of Chinese Medicine

Abstract

Background: With the overwhelming acceptance of evidence-based medicine, valid placebo device or placebo procedure become one of the key issues for randomization and placebo-controlled design clinical trials on the validation of treatment modalities. However, few have been developed for Pediatric Tuina (PT) which is a therapeutic massage for children. Blinding both the recipients and the clinical researcher is considered essential for good research practice. Up to now, no well recognized placebo device or procedure for PT has been reported. We developed a Cloak Shaped Device (CSD) , and design a RCT to detect whether the device is effective as a placebo in PT researches.

Methods: This is a two-arm, parallel-group RCT, while participants and researchers will be blinded. Sixty eligible children will be randomly assigned to genuine Tuina or sham Tuina group with the informed consent signed by their guardians. During the process of Tuina, a CSD will be used to cover the children's body so that the children, guardians, observers and researchers will be blinded. Guardians and observers will be asked to ascertain whether they could differentiate genuine Tuina from sham Tuina. The primary outcomes are the accuracy judgment rates based on guardians' and observers' evaluations of the type of Tuina that participants actually received.

Discussion: This study will contribute to the development of a valid placebo device which can be applied in RCTs regarding pediatric Tuina.

Keywords: placebo procedure; device; sham control; Pediatric Tuina; Chinese pediatric massage.

Background

Blinding is one of the important methodological elements in randomized clinical trials (RCTs) based on the principles of evidence-based medicine[1,2]. A valid placebo device or procedure may successfully avoid the stakeholders from detecting the group allocation situation[3,4,5]. Blinding can minimize the placebo effect as much as possible, therefore the efficacy of the intervention can be evaluated with large extent. Besides, in the trial design, placebo or sham control can not only provide a valid comparator, but also can well control the unknown variables in order to decrease the bias and show the contrasting efficacy of intervention[6].

Placebo has been used in the pharmaceutical clinical trials frequently. In decades, researchers attempted to develop valid sham controls for non-pharmaceutical therapies in Chinese Medicine (CM), including acupuncture[16][17][18], moxibustion[19] and cupping[20]. However, in trials adopting non-pharmaceutical interventions, the placebo or sham-therapy have yet been well recognized. Difficulties in the development of placebo devices or placebo procedures of non-pharmacological regimens may occur when participants have had similar experiences[7,8], or when the placebo procedure is not rationally established, expectation bias may easily be introduced[9]. Therefore, to develop appropriate devices for sham massage or sham Tuina is warranted.

PT is a form of traditional Chinese medicine(TCM) therapy in which trained practitioners manually stimulate specific acupoints of the body which are located primarily on the fingers, palms, arms, head, abdomen and back. It has been a valuable option for children's health promotion since more than one thousand years ago (652 AD) and it is still widely used nowadays in the prevention or treatment of various kinds of pediatric diseases, such as diarrhea, dyspepsia, pneumonia[15]. Although some studies showed that PT is effective with few side effects[12,13,14]. More rigorous designed trials are needed to evaluate the efficacy of PT. The main obstacle in this field is to develop a valid placebo device or procedure which can make the sham Tuina comparison possible. In this study, we will evaluate the validity of a newly developed Cloak Shaped Device (CSD) for sham PT.

[figure not shown]
Methods

Study design

We will use the randomized controlled design to assess the validity of the CSD for sham PT. The primary outcomes are the accuracy judgement rates based on guardians' and observers' evaluations of the type of Tuina that participants actually received.

One of the guardians for each child will be informed with all the information of the trial before the child is included. They will be told that their children may receive genuine PT or sham PT. Once the informed consent signed, eligible children will be randomly assigned to genuine PT or sham PT group with 1:1 ratio. Computer generated randomization lists will be concealed in the opaque envelopes, which performed by irrelevantly authorized expert from the department of medical statistics of The 2nd Affiliated Hospital of Guangzhou University of Chinese Medicine.

Trained practitioners will manually do 15 minutes session of Tuina on each participant while the guardians and observers are watching. The guardians and observers will be required to record their judgements of the type of Tuina, either it is genuine or sham PT, that the participant actually received. If the child is equal to or older than 3 years old, researchers will ask the child some questions in terms of the experience of Tuina after they finish the Tuina procedure.

Study population

Children will be recruited at the outpatient department of pediatrics in Dongguan Kanghua hospital which is a tertiary A western medicine hospital located in Dongguan, Guangdong province, China.

Inclusion criteria:

- Children with disease in Pediatric Outpatient Department of Kanghua Hospital
- Children aged 0-6 years.
- Guardian and child can be cooperative over the study period.
- Guardian signed the informed consent.
- Children have no attendance in other studies simultaneously.

Exclusion criteria:

- Child with one or more PT experiences on arms, abdomen or back.
- Child with a previous history of convulsion.
- Child with any of the following conditions on the area to be manipulated: phlebitis, open wound, fracture and tissue damage.
- Child combined with any of following conditions: disorders of consciousness, seizures or twitching, shock, varicella, hand-foot-mouth disease, encephalitis B, and etc.

Sample size

The aim of this study is to evaluate the validity of CSD whether it may have a balanced accurate rate (e.g. 50%) on the type of Tuina that the child actually received in the genuine or sham group, when judged by guardians and observers, respectively. About 95% of the subjects can distinguish the genuine and sham pediatric Tuina accurately without placebo device in the clinical practice. Based on the results from the previous similar researches, an ideal blinding device will be considered have

a good blinding effect while the accurate rate of subjects (genuine group or sham group) on guessing the Tuina type is 50%. Therefore, we adopt the single-sample test in the software of PASS 11.0 (NCSS LLC) to calculate the sample size, and set accurate rate of subjects with 95% in non-blinding status, and 50% in blinding status, powered by 90%, and significance level with 0.05. After the calculation, 24 subjects of each group are needed, on account of the 20% subject may drop out, the finally sample size is 60 subjects in total with 30 subjects in each group.

Development of the CSD

The CSD is made of opaque cotton cloth in cloak-shape. It is big enough to cover the upper body, including upper limbs and trunk, of a child who is 6 year-old or under old. Two narrow holes are present for therapists to insert their hands through and perform Tuina. The entire manipulation process will be covered by the CSD. Blinding will be maintained during the whole study process.

Genuine pediatric Tuina and sham pediatric Tuina

All the techniques and acupoints will be the same in both group, the only difference is that on whose skin that the manipulation will be performed. For Genuine PT the manipulation will be performed on the children's skin directly. However, in the Sham PT group, the therapist will put their own hand above the same skin areas as those in the Genuine PT group and do the Tuina with the other hand of their own. Five acupoints located on the upper limbs and the trunk are involved in both Tuina group, including Neibagua, Banmen and Dachang on hands, Fu on the abdomen, and Qijiegu on the sacroiliac region. The frequency of the techniques are as normal with 150 times per minute for Neibagua, 200 times per minute for Banmen, Dachang, and Qijiegu, 80 times per minute for Fu. The acupoints, manipulation time and frequency are the same for all subjects in two groups. All manipulations will be carried out with light, fast, and soft touch, and coconut oil will be used to protect children's skin in both groups.

Effective measurements

Primary Outcome Measures

- Accurate judgement rate of the guardians' estimation
- Accurate judgement rate of the observers' estimation

Secondary Outcome Measures

- Verbal Rating Scale (VRS) of parent's attitude towards pediatric Tuina (We use the VRS-4 with the higher score representing the more positive attitude to evaluate the degree of the awareness and reliability of the parents towards pediatric Tuina.)
- VRS of Children's Perception of Pediatric Tuina (Verbal Rating Scale, VRS). (We use the VRS-4 with the higher score representing the more positive attitude to evaluate the degree of the perception of the children equal or more than 3 years old during and after the Tuina.)
Children equal or more than 3 years old in both genuine Tuina and sham Tuina groups will evaluate their sensation, such as pain, warm, discomfort, itch, et al.
- VRS of Parent's Attitude Towards Pediatric Tuina From the Observers' Perspectives. (Verbal Rating Scale, VRS)(We use the VRS-4 with the higher score representing the more positive attitude to evaluate the degree of the reliability of the parents towards pediatric Tuina from the observers' perspectives.)

- Compliance of guardians and children on three continuous PT therapies. (Verbal Rating Scale, VRS)(We use the VRS-5 with the higher score representing the more positive attitude to follow three continuous PT therapies.)

Ethics

The study will respect the Helsinki declaration. It has been approved by the ethics committee of Guangdong Provincial Hospital of Chinese Medicine(Z2017-212-01) and DongGuan Kanghua Hospital(2018003), and has been registered on the ClinicalTrials.gov (Identifier: NCT03474172)before the recruitment of subjects. Informed consent must be endorsed by one guardian of each child if the child is going to attend the trial. All the participants will receive a bonus for the traffic when they complete the trial.

Statistical analysis

All the data in this study will be recorded in a case report form (CRF). When the trial is complete, data will be entered into the database by double entry method. We will use Wilcoxon rank sum test analysis for abnormal distribution data, Mann-Whiney U test for ranked outcomes and chi-squared test for binary outcomes.

In the primary outcome, we will calculate accurate judgment rates on type of Tuina the participants received by guardians and observers, respectively.

In the secondary outcomes, Mann-Whiney U test will be used for the comparison of Verbal Rating Scale (VRS) of parent's attitude towards pediatric Tuina, VRS of Children's Perception of Pediatric Tuina, VRS of Parent's Attitude Towards Pediatric Tuina from the Observers' Perspectives, Compliance of guardians and children in terms of three continuous PT therapies between groups.

Simple Kappa Coefficient will be used to analysis the agreement of the judge results and the attitude towards PT between the guardians and observers. We will use Chi-square test to identify the influence factor, including the education level, age, Children's Perception, parent's attitude, et al.

Statistical Packages of Social Sciences (SPSS) for Windows version 18.0 (Chicago, IL) will be used to conduct the analyses. For all tests, two-tailed P value less than 0.05 is considered as statistically significant.

The Kappa coefficient ranges from 0 to 1.0. In the study, we define if the coefficient value is less than 0.2, it presents that the agreement is slight. If it ranges from 0.21-0.40 indicates the agreement is weak; ranging from 0.41-0.60 means the agreement is moderate; ranging from 0.61-0.80 implies the agreement is favorable. And for those range from 0.81-1.00 it represents that the agreement is perfect.

Quality monitoring

All the researchers will be trained before the trial conducted, including the communication skills with guardians and children, subjects screening, randomization and evaluation procedure. Meanwhile, three experienced therapists will receive a well-designed session of manipulation technical training course to reach a high level of standardization. Detail information on dropout, adverse event of subjects will be recorded on the CRF. During the study period, supervisors will check the CRF aperiodically.

Discussions

To our knowledge, this trial is the first study aiming for the validity of a placebo device in regards of sham PT. On the basis of a rigorous randomized controlled design of our study, the results may provide

evidence for CSD on whether it is worthy to be applied as a useful placebo device for the evidence-based researches of pediatrics when PT or other similar massage interventions will be adopted.

Despite PT, other non-pharmaceutical therapies of Chinese Medicine have developed some sham or blinding methods, such as several types of sham acupuncture or sham cupping devices. The effects of these methods have been revealed by adopting similar research design as this study[16,21-23].

PT has been found to be easily accepted by children based on the light and gentle technique with good safety record. Up to now, none severe adverse event due to PT was reported, some mild adverse events such as skin abrasion can be easily avoided with clear and correct operating instructions. Therefore, guardians and children are very likely to have good compliance to complete the trial. We assume children less than 6 years old cannot differ the genuine PT and sham PT when they are lack of former experience of PT, and consequently the placebo effect for both groups will not be generated systematically. In this case, guardians' and observers' judgements will be more important than children's own perspective in the validation evaluation of the CSD.

In conclusion, this trial may provide valuable evidence on placebo device for the future RCTs in terms of PT or other similar kinds of massage.

Declarations

Ethics approval and consent to participate

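### Does the exclusion for earlier Tuina experience miss the hands, where three of the five study acupoints lie?

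*Combined protocol and SAP*

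**What the plan says.** Under Study population, Exclusion criteria, earlier exposure is handled by one line: "Child with one or more PT experiences on arms, abdomen or back". Another line in the same list defines its site by reference to the treatment: "Child with any of the following conditions on the area to be manipulated".

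The section on genuine and sham Tuina introduces the treatment with "Five acupoints located on the upper limbs and the trunk are involved in both Tuina group" and then gives the sites: "including Neibagua, Banmen and Dachang on hands, Fu on the abdomen, and Qijiegu on the sacroiliac region". The Background describes PT acupoints in general as "located primarily on the fingers, palms, arms, head, abdomen and back".

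Two passages explain why earlier exposure matters. The Background says that difficulties with sham procedures "may occur when participants have had similar experiences". The Discussions section assumes that children under 6 "cannot differ the genuine PT and sham PT when they are lack of former experience of PT".

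The primary outcomes are the accuracy of the guardians' and of the observers' judgements. The child's own view enters as a secondary outcome: "Children equal or more than 3 years old in both genuine Tuina and sham Tuina groups will evaluate their sensation".

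**The concern.** The criterion does not mention the site that holds most of the study acupoints. The Background treats fingers and palms as separate from arms, so a screener who takes the protocol's vocabulary at face value could admit a child with hand-only experience. Two screeners could also decide differently about the same child. The neighbouring exclusion, tied to the treated area, shows that a wording without this weakness was available.

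There is a second apparent mismatch. The assumption in the Discussions has no limit by body site, while the criterion does. A child whose earlier PT was on the head alone is eligible however *arms* is understood.

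In the sham group the therapist works on their own hand, held over the child's skin. A child who knows PT on the hands might notice the difference. That could affect the perception ratings of children aged 3 or older and weaken the assumption that children cannot tell the two procedures apart.

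**Working it through.** The plan states no figure on this point, and the only arithmetic is a count. The rest is a comparison of passages.

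**Step 1: acupoints by site** (section on genuine and sham Tuina). Hands 3 (Neibagua, Banmen, Dachang), abdomen 1 (Fu), sacroiliac region 1 (Qijiegu); 3 + 1 + 1 = 5. The reading of *arms* therefore decides 3 of the 5.

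**Step 2: criterion against treatment.**

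| Order | Zone in the exclusion | Zone treated |
|---|---|---|
| 1 | arms | hands (introduced as upper limbs) |
| 2 | abdomen | abdomen |
| 3 | back | sacroiliac region |

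The two lists match in number and order. If *arms* left out the hands, the criterion would screen for a region with no study acupoint and ignore the region with three. With *arms* as the whole upper limb, every treated zone is covered. The one site in the Background list then left out is the head, which is also the one site that the study does not treat. The description of the cloak likewise speaks of upper limbs and trunk. The Background list, by contrast, is a general account of PT and does not define terms for eligibility.

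**Step 3: who could slip through on the literal reading.** Only a child whose earlier PT never touched arms, abdomen or back. A session like the study's own includes Fu on the abdomen, so it excludes the child under every reading. The documents do not say how many hand-only children attend this clinic.

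**Step 4: which outcomes could be affected.** Guardians and observers make the primary judgements while the manipulation is hidden under opaque cloth. A child's hand-only experience could reach them only through the child's reactions, or through a guardian who had watched earlier sessions. The direct route is to the perception rating in children aged 3 or older. The Discussions section ranks the guardians' and observers' judgements above the child's own view.

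**Step 5: the head-only case.** The Background worries about similar experience, and a rule limited to the treated regions is a reasonable way to apply that. The sentence in the Discussions is a general assumption, not an eligibility rule. Excluding all earlier PT would match it word for word but would shrink the eligible pool, to screen out experience at a site that the study never touches.

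**The case for a change.** The strongest case for a change is that eligibility wording should not depend on inference. No passage defines *arms*, the Background separates it from fingers and palms, and the content of the screening training mentioned under Quality monitoring is not given. The protocol itself names earlier similar experience as a threat to sham procedures, and the Abstract counts the children among those to be blinded. A few added words would remove the doubt at almost no cost. Randomisation would be expected to spread any hand-experienced children over both groups, but it would not stop such a child in the sham group from noticing the difference.

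The ambiguity stands as a matter of drafting, and so does the limit on what randomisation can do. The step from ambiguity to harm does not. It requires screeners to choose the reading that makes the criterion pointless for three of the five acupoints, and it requires children with hand-only experience to be present in numbers that matter. The documents support neither. The added words would record what the criterion most plausibly already means, with no demonstrated gain for any result.

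**Conclusion.** This is loose wording that those applying the plan can be expected to fill sensibly, and no change is needed. Three of the five acupoints do lie at a site that the criterion does not name, but the zone-by-zone match with the treatment makes the inclusive reading much the likelier one. Under that reading all five treated sites are covered.

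Any remaining effect is confined to one secondary rating in children aged 3 or older whose only earlier PT avoided arms, abdomen and back. Its size cannot be calculated, because the documents give neither the share of such children nor how their experience would change the ratings. No effect on either primary outcome is shown. Leaving head-only experience out of the exclusion is a fair trade-off between strictness and the size of the eligible pool.

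The conclusion assumes that trained staff at the one recruiting hospital read *arms* as the upper limb and *back* as including the sacroiliac region. The documents make both readings natural but do not state them.

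### The primary accuracy rates have no stated contrast or success rule, and the by-arm 50% benchmark mixes a lean in guessing with detection of the allocation

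*Combined protocol and SAP*

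**What the plan says.** The relevant text is in three sections of the combined protocol and SAP.

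- **Sample size.** The aim is "a balanced accurate rate (e.g. 50%) on the type of Tuina that the child actually received in the genuine or sham group", judged by guardians and by observers. Blinding is called good when "the accurate rate of subjects (genuine group or sham group) on guessing the Tuina type is 50" per cent. For the single-sample calculation the authors "set accurate rate of subjects with 95% in non-blinding status, and 50% in blinding status", with 90% power and a 0.05 level. The result is that "24 subjects of each group are needed, on account of the 20% subject may drop out", giving 30 per group.
- **Study design.** Each judge records one of two answers, "either it is genuine or sham PT". No third option is mentioned. The session is given "on each participant while the guardians and observers are watching".
- **Statistical analysis.** For the primary outcome, "we will calculate accurate judgment rates on type of Tuina the participants received by guardians and observers, respectively". Elsewhere the section lists a "chi-squared test for binary outcomes" without naming a table, and sets a two-tailed 0.05 level for all tests. It names a between-group test for each secondary rating scale and gives interpretation bands for kappa. The kappa measures agreement between guardians and observers, not whether either can tell the allocation.

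**The concern.** Whether the cloak blinds is the question the trial exists to answer. The analysis section gives the primary rates no reference value, contrast, interval or tolerance, and does not say whether guardians and observers must both succeed. If the rule is settled after the data are seen, the same counts can support different conclusions.

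The benchmark that the Sample size section does supply, 50% accuracy worded by arm, has its own weakness. With two permitted answers, accuracy in one arm depends on whether the guardian or observer can tell and on which answer he or she favours. A cloak that hides everything can miss 50% in both arms only because judges tend to say genuine. A wrong verdict in either direction would carry into later sham-controlled trials that use the device.

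**Working it through.** **Inputs.** From the documents: 30 per arm, 24 per arm after 20% dropout, benchmarks 50% and 95%, two-sided 0.05, a two-way answer. Assumed: the lean q (50% to 80%), the illustrative accuracies, and independent judgements. Tests are exact two-sided binomial for one proportion and Pearson chi-squared for two; intervals for differences are Newcombe.

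**1. The plan's own figure.** The dropout step reproduces: 24 / (1 − 0.20) = 30. The 24 does not reproduce from a single-sample test of 95% against 50% (exact binomial gives 7 to 12, z formulas 4.9 to 9.9). A two-sample test with continuity correction gives 23. Nothing below depends on this; at 24 the single-sample contrast has power above 99.9%.

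**2. What by-arm accuracy measures.** Accuracy in genuine = P(says genuine | genuine). Accuracy in sham = 1 − P(says genuine | sham). If nobody can tell, both conditional probabilities equal q, so the accuracies are q and 1 − q. The difference in the proportion judged genuine is

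P(says genuine | genuine) − P(says genuine | sham) = accuracy in genuine + accuracy in sham − 1 = q + (1 − q) − 1 = 0,

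whatever the lean.

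**3. Each arm against 50%, for a cloak that gives no information.** The test does not reject at 10 to 20 of 30, or at 7 to 17 of 24. By symmetry both arms reject with the same probability a, so P(at least one rejects) = 1 − (1 − a)². At q = 70% and 30 per arm, a = 0.589 and 1 − 0.411² = 0.83.

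| Assumed lean q | 50% | 60% | 70% | 80% |
|---|---|---|---|---|
| 30 per arm | 8% | 32% | 83% | 99.6% |
| 24 per arm | 4% | 18% | 63% | 96% |

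Example: 21/30 correct in genuine and 9/30 in sham. Each arm differs from 50% (p = 0.043). Yet 21/30 are judged genuine in both arms, a difference of 0 (95% CI −0.22 to 0.22).

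**4. The two benchmarks against each other.** At 30 per arm, 25 or fewer correct is significantly below 95%, and 21 or more is significantly above 50%. So 21 to 25 correct (70% to 83%) is both. At 24 per arm the overlap is 18 to 20, or 18 to 19 if 0.025 is required in the lower tail.

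Example with no lean: 24/30 correct in both arms. Against 95%, p = 0.003; against 50%, p = 0.001. The proportions judged genuine are 24/30 and 6/30, a difference of 0.60 (95% CI 0.36 to 0.75).

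**5. Chi-squared on accuracy between arms.** A device with 80% accuracy in both arms has equal accuracies, so it is flagged in only about 5% of trials at either size, although judges can clearly tell.

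**6. Tests that separate lean from detection.** With equal arms, pooled accuracy and judgement by allocation both do so. A non-significant result still does not show blinding. Share of trials at 30 per arm in which each test misses a partly unblinded device:

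| True accuracy, both arms | Pooled accuracy v 50% | Judgement by allocation |
|---|---|---|
| 70% | 16% | 10% |
| 60% | 74% | 65% |

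**The case against.** The best defence is that the plan is not silent. It names a 50% target, a single-sample test for sizing, a generic chi-squared test and a two-sided level. It also collects every judgement, so if rates are reported by arm, anyone can add them and subtract one. That is right as far as it goes: no data are lost, and the gap is in specification and interpretation. But none of these elements is tied to the primary rates as a contrast or success rule.

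A second defence is that the competing readings are not equally strong. This stands. The plan nowhere says that accuracy below 95% means blinded; 95% appears only as a sizing input, though a single-sample test of 95% against 50% makes it a possible null. Nor does it say that equal accuracy in the two arms is enough: 50% is written next to the word balanced, so 80% in both arms would miss the stated target. A reader might infer that the plan endorses several rules of equal standing; the documents do not support that.

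Third, the lean is assumed. This also stands. The documents give no lean, so the 83% must not be read as a forecast; with no lean the figure is 8%. The conflict between the two benchmarks needs no lean.

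A reader might also infer that pooled accuracy or judgement by allocation, simply tested, would settle the matter. It would not, as the miss rates for 70% and 60% accuracy show.

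**Conclusion.** The concern holds. The primary outcome has a target but no analysis rule, and the target as worded by arm can fail a cloak that reveals nothing: at least one arm rejects 50% in 8% to 99.6% of trials at 30 per arm, and 4% to 96% at 24, as the assumed lean goes from 50% to 80%. The weaker 95% reading contradicts the 50% target for 21 to 25 correct of 30. The weaker between-arm reading almost never detects a device with 80% accuracy in both arms.

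The by-arm figures rest on an assumed lean and all rates on independent judgements; the identity in step 2 and the overlap in step 4 rest on neither. Two further inferences are not supported. The trial is not shown to be undersized for its single-sample contrast, although that contrast says nothing about showing accuracy close to 50%. Nor is clustering by observer a demonstrated defect, because the documents do not say how many observers there are.

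**What to change.** For guardians and observers separately, make the primary analysis the 2×2 table of judgement (genuine or sham) by actual allocation.

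- Report the difference between arms in the proportion judged genuine, with a 95% CI.
- Report accuracy, or the blinding index 2 × accuracy − 1, with a CI in each arm to show any lean.
- Before unblinding, state and justify the limit the CI must meet, and whether both judge types must meet it. If no limit can be justified, report the difference and CI as an estimate only.
- Do not rest the conclusion on a per-arm test against 50% or 95% alone, on a between-arm test of accuracy, or on a non-significant result.

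No extra children or data are needed. The cost is limited precision. For a cloak that gives no information (lean 50% to 80%), the CI lies inside the limit in this share of trials, per judge type and with independent judgements:

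| Illustrative limit | 30 per arm | 24 per arm |
|---|---|---|
| ±0.30 | 48–67% | 33–51% |
| ±0.40 | 84–96% | 69–89% |

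These limits only show what the sample can deliver and are not recommendations. A difference of 0.40 corresponds, for example, to 70% accuracy in both arms (0.70 + 0.70 − 1). Requiring both judge types to pass lowers the rates.

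Optional: state the number of observers and, if the same observers judge several children, use a CI that allows for it.
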